#### **10.4 Vital Signs**

Vital sign measurements of systolic and diastolic blood pressures (sitting and standing), pulse rate (sitting and standing), respiratory rate, temperature, weight, orthostatic systolic blood pressure, orthostatic diastolic blood pressure, and orthostatic pulse rate will be summarized. Orthostatic vital sign values (orthostatic systolic and diastolic blood pressures, and orthostatic pulse rate) are defined as the corresponding standing measurement minus sitting measurement of systolic and diastolic blood pressures and pulse rate respectively.

Each vital sign variable will be summarized for all time points (starting with Baseline) with the number of non-missing observations, mean and standard deviation, median, Q1, Q3, minimum and maximum. Mean change from baseline to each applicable post-baseline visit will be summarized for each vital sign variable, with the number of observations, baseline mean, and visit mean. The change from baseline mean, standard error will be presented for the mean change from baseline within each treatment group.

Vital sign variables will be evaluated based on PCS criteria ([Table 17](#)). For each vital sign PCS criterion, the number and percentage of participants who have a vital sign value meeting the criteria will be summarized. Listings will be provided to summarize subject-level vital sign data for participants meeting PCS criteria. In addition, a tabular display showing all AEs that occurred in participants who had PCS postbaseline vital sign values will be provided.

## **10.5 Other Safety Analyses**

### **10.5.1 Electrocardiogram**

Descriptive statistics for ECG parameters (i.e., heart rate, PR interval, QRS interval, RR interval, QT interval, and QTc interval) at baseline, postbaseline, and changes from baseline values at each postbaseline timepoint will be presented by treatment group.

ECG parameter values are considered PCS if ECG values meet either the actual value or change from baseline PCS high criteria listed in [Table 18](#). The number and percentage of participants with PCS postbaseline values will be tabulated by study treatment. The percentages will be calculated relative to the number of participants with an available non-PCS baseline value and at least 1 postbaseline assessment. The numerator will be the total number of participants with an available non-PCS baseline value and at least 1 PCS postbaseline ECG value during the study. A supportive listing of participants with PCS postbaseline values will be provided. A listing of all AEs for participants with PCS ECG values will also be provided.

To evaluate ECG postbaseline values of clinical interest, the number and percentage of participants with post-treatment QTcF  $> 450$  msec,  $> 480$  msec, and  $> 500$  msec will be tabulated by treatment group.

The number and percentage of participants with an increase  $> 30$  msec but  $\leq 60$  msec, and with an increase  $> 60$  msec in QTcF will be tabulated. Participants will be counted only once for the most severe category. A supportive listing of participants with postbaseline QTcF increases  $> 30$  msec will be provided, including the PID number, study center, and all QTc values (including changes from baseline). A listing of all AEs for participants with postbaseline QTcF increases  $> 30$  msec will also be provided.

A shift table from baseline to the end of double-blind treatment period in the investigator's overall interpretation of the ECG will be presented by treatment group for the following categories: normal; abnormal, not clinically significant; abnormal, clinically significant.

A tabular display of participants with postbaseline clinically significant ECG abnormalities according to the investigator's overall interpretation will be provided.

### **10.5.2 Columbia-Suicide Severity Rating Scale**

For C-SSRS, the number and percentage of participants with suicidal ideation or suicidal behavior as recorded on the C-SSRS will be summarized by treatment group for the Safety Population. The distribution of responses for most severe suicidal ideation and most severe suicidal behavior in the participant's lifetime history, in the past 6 months, in the double-blind treatment period, and in the follow-up period will also be presented by treatment group. Supportive listings will be provided and will include the PID number, study center number, treatment group, lifetime history, and postbaseline values. Intensity of suicidal ideation and suicidal behavior type will also be included in these listings. A listing of all AEs occurring in participants who have suicidal ideation or suicidal behavior will also be provided.

## **11.0 Other Analysis**

### **11.1 Healthcare Resource Utilization Questionnaire**

Healthcare resource utilization questions will include use of migraine-specific healthcare resources due to migraine attack. The number and percentage of participants who visit to any general practitioner, specialist, emergency room, or hospital, and any diagnostic procedures prescribed by health care providers will be provided by treatment group over the past 12 weeks and since last visit, respectively, for the Safety Population. In addition, total number of days spent in the hospital for all admissions during a specific period will be provided by treatment group for Safety Population.

## **12.0 Interim Analyses**

No interim analysis is planned for this study.

## **12.1 Data Monitoring Committee**

An independent DSMB will be established to review unblinded safety data and summary reports, identify any safety issues and trends, and make recommendations to AbbVie, including modification or ET of the study, if emerging data show unexpected and clinically significant AEs of treatment.

Details of the DSMB memberships, standard operational procedures for data monitoring/review, frequency of review, and other pertinent details will be provided in a separate DSMB Charter.

## **13.0 Overall Type-I Error Control**

A fixed-sequence procedure will be used for multiple comparisons to control the family-wise Type I error rate at a 0.05 level. Once the primary endpoint for atogepant dose is significant at 0.05 (2-sided), the secondary endpoints will be tested. The testing sequence is specified for the US and EU in [Table 6](#) and [Table 7](#).

**Table 6. Multiple Comparisons Procedure Definitions for the Submission in the US**

Nodes	Alternate Hypothesis	Weight	Initial Local Significance Level
P1	Atogepant 60 mg is significantly different from placebo in change from baseline in mean monthly migraine days across the 12-week treatment period	1	$\alpha$
S1	Atogepant 60 mg is significantly different from placebo in the achievement of at least a 50% reduction in mean monthly migraine days across the 12-week treatment period	0	$\alpha \times 0 = 0$
S2	Atogepant 60 mg is significantly different from placebo in change from baseline in mean monthly headache days across the 12-week treatment period	0	$\alpha \times 0 = 0$
S3	Atogepant 60 mg is significantly different from placebo in change from baseline in mean monthly acute medication use days across the 12-week treatment period	0	$\alpha \times 0 = 0$
S4	Atogepant 60 mg is significantly different from placebo in change from baseline in the MSQ v2.1 Role Function Restrictive domain score at Week 12	0	$\alpha \times 0 = 0$
S5	Atogepant 60 mg is significantly different from placebo in change from baseline in mean monthly Performance of Daily Activities domain score of the AIM-D across the 12-week treatment period	0	$\alpha \times 0 = 0$
S6	Atogepant 60 mg is significantly different from placebo in change from baseline in mean monthly Physical Impairment domain score of the AIM-D across the 12-week treatment period	0	$\alpha \times 0 = 0$

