9.4.1.3. Secondary Analyses

The secondary endpoints for headache days, acute medication use days, MSQ v2.1 Role Function-Restrictive domain score, Performance of Daily Activities domain score of the AIM-D, Physical Impairment domain score of the AIM-D, and HIT-6 total score will be analyzed in the same manner as that used to analyze the primary endpoint.

The 50% responder, defined as a participant with at least a 50% reduction from baseline in the 3-month average of monthly migraine days, will be assessed for each individual. A logistic regression model will be used to analyze the proportion of 50% responders across the 12-week treatment period. This model assumes a binary distribution for the response and uses a logit link. The analysis model will include treatment group, region, and number of classes of failed prior prophylactic treatments as categorical fixed effects; baseline value will be included as a covariate. The analysis will be performed based on all postbaseline values using only the observed cases without imputation of missing values. The treatment difference in terms of odds

ratio between each atogepant dose group and placebo will be estimated and tested from this model.

The overall type I error rate for the primary and secondary efficacy endpoints will be controlled at the 0.05 level using the fixed sequence procedure following the testing order pre-specified in [Table 9-1](#) for the United States and [Table 9-2](#) for the EU. Once one efficacy endpoint is not significant, all subsequent endpoints will not be tested.

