**Table 7. Multiple Comparisons Procedure Definitions for the European Submissions**

Nodes	Alternate Hypothesis	Weight	Initial Local Significance Level
P1	Atogepant 60 mg is significantly different from placebo in change from baseline in mean monthly migraine days across the 12-week treatment period	1	$\alpha$
S1	Atogepant 60 mg is significantly different from placebo in $\geq 50\%$ reduction in 3-month average of monthly migraine days	0	$\alpha \times 0 = 0$
S2	Atogepant 60 mg is significantly different from placebo in change from baseline in mean monthly headache days across the 12-week treatment period	0	$\alpha \times 0 = 0$
S3	Atogepant 60 mg is significantly different from placebo in change from baseline in mean monthly acute medication use days across the 12-week treatment period	0	$\alpha \times 0 = 0$
S4	Atogepant 60 mg is significantly different from placebo in change from baseline in the HIT-6 total score at Week 12	0	$\alpha \times 0 = 0$
S5	Atogepant 60 mg is significantly different from placebo in change from baseline in the MSQ v2.1 Role Function Restrictive domain score at Week 12	0	$\alpha \times 0 = 0$

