**Table 8. Summary of Collection Devices for Primary and Secondary Endpoints for Submission in the US**

Hypothesis Testing	Node	Endpoint	Collection Device
Primary	P1	Change from baseline in mean monthly migraine days across the 12-week treatment period	eDiary
Secondary 1	S1	Change from baseline in mean monthly headache days across the 12-week treatment period	eDiary
Secondary 2	S2	Change from baseline in mean monthly acute medication use days across the 12-week treatment period	eDiary
Secondary 3	S3	Achievement of at least a 50% reduction in mean monthly migraine days across the 12-week treatment period	eDiary
Secondary 4	S4	Change from baseline in MSQ v2.1 Role Function Restrictive domain score at Week 12	eTablet
Secondary 5	S5	Change from baseline in mean monthly Performance of Daily Activities domain score of the AIM-D across the 12-week treatment period.	eDiary
Secondary 6	S6	Change from baseline in mean monthly Physical Impairment domain score of the AIM -D across the 12-week treatment period.	eDiary

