**Table 9. Summary of Collection Devices for Primary and Secondary Endpoints for European Submissions**

Hypothesis Testing	Node	Endpoint	Collection Device
Primary	P1	Change from baseline in mean monthly migraine days across the 12-week treatment period	eDiary
Secondary 1	S1	Change from baseline in mean monthly headache days across the 12-week treatment period	eDiary
Secondary 2	S2	Change from baseline in mean monthly acute medication use days across the 12-week treatment period	eDiary
Secondary 3	S3	Achievement of at least a 50% reduction in mean monthly migraine days across the 12-week treatment period	eDiary
Secondary 4	S4	Change from baseline in HIT-6 total score at Week 12	eTablet
Secondary 5	S5	Change from baseline in MSQ v2.1 Role Function Restrictive domain score at Week 12	eTablet

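### Do the node labels in SAP Tables 8 and 9 create a second, conflicting testing order for the secondary endpoints?

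*SAP*

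**What the plan says.** SAP Section 13.0 states: "A fixed-sequence procedure will be used for multiple comparisons to control the family-wise Type I error rate at a 0.05 level". It then says where the order is found: "The testing sequence is specified for the US and EU in" Tables 6 and 7. In Table 6 (US), node S1 is the responder endpoint: "Atogepant 60 mg is significantly different from placebo in the achievement of at least a 50% reduction in mean monthly migraine days". Node S2 is headache days and S3 is acute medication use days. Table 7 (Europe) has the same first three, with S1 worded as at least a 50% "reduction in 3-month average of monthly migraine days". Protocol Section 9.4.1.3 gives the stopping rule, "Once one efficacy endpoint is not significant, all subsequent endpoints will not be tested", and takes its order from protocol Tables 9-1 and 9-2.

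SAP Section 14.1, on COVID-19, contains two further tables with columns for hypothesis number and node. The second row of Table 8 (US) reads "Secondary 1 S1 Change from baseline in mean monthly headache days across the 12-week treatment period eDiary". The responder comes two rows later, and Table 9 (Europe) has it in the same place: "Secondary 3 S3 Achievement of at least a 50% reduction in mean monthly migraine days across the 12-week treatment period eDiary".

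**The concern.** In a fixed-sequence procedure nothing protects the error rate except an order settled in advance. The SAP attaches one set of labels, S1 to S3, to two different orders, in both the US and the European tables. This is current version 2.0 text, not an entry in a change log.

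Tables 8 and 9 are also more than unnumbered lists, because they carry the vocabulary of the multiplicity procedure. Tables 6 and 7 give every secondary a weight of zero and show no transition weights, so within them the order rests on node labels and row position.

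If both orders were live, a miss on headache days or acute medication use days would leave the responder result confirmed under one and untested under the other. If the choice stayed open until after unblinding, the error rate would no longer be held at 0.05.

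**Working it through.** **Which tables set the order.** The first three secondaries, place by place:

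| Place | First | Second | Third | Role given by the text |
|---|---|---|---|---|
| Protocol Tables 9-1 and 9-2 | responder | headache days | acute medication days | testing order (protocol 9.2 and 9.4.1.3) |
| SAP Tables 1 and 2 | responder | headache days | acute medication days | testing order used for power (SAP 2.4) |
| SAP Table 5 | responder | headache days | acute medication days | estimand attributes |
| SAP Tables 6 and 7 | responder | headache days | acute medication days | testing sequence (SAP 13.0) |
| SAP Tables 8 and 9 | headache days | acute medication days | responder | collection devices (SAP 14.1) |

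From S4 onward, Tables 8 and 9 agree with Tables 6 and 7. Every place that the text designates as setting the order gives the same one. Tables 8 and 9 contain no hypotheses, weights or significance levels, and no sentence sends the reader to them for the sequence. SAP Section 15.1 lists two departures from the protocol's planned analyses (the diary-day threshold and the subgroups). A new testing order is not among them.

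**Reproducing the stated powers.** The plan gives 150 per arm and 15% dropout, so n = 150 × 0.85 = 127.5 per arm, with two-sided alpha 0.05. For a difference d with standard deviation s, power is approximately Φ(d / (s√(2/n)) − 1.96). For the US primary endpoint, 1.7 / (3.5 × √(2/127.5)) = 3.878, and Φ(1.918) = 97.2%, against 97% stated. A two-proportion calculation serves for the responder.

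| Endpoint | US stated | US computed | EU stated | EU computed |
|---|---|---|---|---|
| Primary | 97% | 97.25% | 95% | 95.45% |
| Responder | 99% | 99.93% | 99% | 99.76% |
| Headache days | 95% | 95.62% | 92% | 93.22% |
| Acute medication days | 97% | 97.15% | 93% | 93.74% |

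The remaining secondaries (with 21% dropout for the AIM-D endpoints) also reproduce to within 2 points.

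**What the order would change if both were live.** Multiply along each chain, under the plan's own independence assumption.

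- Responder tested first after the primary: US 0.9725 × 0.9993 = 97.2%; EU 0.9545 × 0.9976 = 95.2%.
- Responder tested third: US 0.9725 × 0.9562 × 0.9715 × 0.9993 = 90.3%; EU 0.9545 × 0.9322 × 0.9374 × 0.9976 = 83.2%.
- Headache days tested second rather than first: 92.9% against 93.0% (US) and 88.8% against 89.0% (EU). Acute medication use days also move by about 0.1 point (US) and 0.2 point (EU).
- Whole chain won: 67.3% (US) and 79.3% (EU) under either order.

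With the stated powers, and given primary success, the two orders would disagree on the responder claim when the responder wins and at least one of the other two misses:

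- US: 0.99 × (1 − 0.95 × 0.97) = 7.8%
- EU: 0.99 × (1 − 0.92 × 0.93) = 14.3%

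These percentages apply only if Tables 8 and 9 are taken as a decision rule. Under Section 13.0 the responder is S1 and the disagreement does not arise.

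**The case for a change.** The best argument for acting is that a reader should not have to work out which table governs. Tables 8 and 9 use the procedure's own node names, and the SAP nowhere says that those names are not the testing order. A programmer or report author working from Table 8 could gate or label the wrong endpoint. If the order really were chosen after unblinding, with the primary passed and both candidate first secondaries truly null, the chance of at least one false claim would be 1 − 0.95² = 9.75% under independence, not 5%.

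What stands is that the labels are wrong and could confuse someone reading Section 14.1 alone. The error-rate argument does not stand, because it needs an open choice and Section 13.0 closes it. Adopting the device-table order would contradict that section, SAP Section 2.4 and protocol Section 9.4.1.3. There is also little to gain by it: the responder claim becomes harder to win, while the other two endpoints gain only 0.1 to 0.2 point of power. The 7.8% and 14.3% figures are probably too high even on their own premise. All three endpoints come from the same daily diary, so positive correlation is likely, and it would make a responder win alongside a miss on another endpoint rarer than independence implies.

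**Conclusion.** The mismatch is real but clerical. A sponsor following the SAP as written tests the responder first, then headache days, then acute medication use days, and family-wise error is held at 0.05. Correcting the labels in Tables 8 and 9 would be harmless tidying. It would alter no test, stated power, sample size or conclusion.

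This rests on two points of reading: that Section 13.0 means what it says in assigning the sequence to Tables 6 and 7, and that Tables 8 and 9 serve only the purpose for which Section 14.1 introduces them. That their numbering is a leftover is an inference, since the documents do not explain it; the conclusion does not depend on it. No change to the plan is called for.

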**Table 7. Multiple Comparisons Procedure Definitions for the European Submissions**

Nodes	Alternate Hypothesis	Weight	Initial Local Significance Level
P1	Atogepant 60 mg is significantly different from placebo in change from baseline in mean monthly migraine days across the 12-week treatment period	1	$\alpha$
S1	Atogepant 60 mg is significantly different from placebo in $\geq 50\%$ reduction in 3-month average of monthly migraine days	0	$\alpha \times 0 = 0$
S2	Atogepant 60 mg is significantly different from placebo in change from baseline in mean monthly headache days across the 12-week treatment period	0	$\alpha \times 0 = 0$
S3	Atogepant 60 mg is significantly different from placebo in change from baseline in mean monthly acute medication use days across the 12-week treatment period	0	$\alpha \times 0 = 0$
S4	Atogepant 60 mg is significantly different from placebo in change from baseline in the HIT-6 total score at Week 12	0	$\alpha \times 0 = 0$
S5	Atogepant 60 mg is significantly different from placebo in change from baseline in the MSQ v2.1 Role Function Restrictive domain score at Week 12	0	$\alpha \times 0 = 0$

## 14.0 COVID-19 Related Analyses

### 14.1 Efficacy Evaluation

#### Efficacy Endpoints

Table 8 and Table 9 describe the collection devices for primary and secondary endpoints for US and EU respectively. For US, the primary endpoint and 5 secondary endpoints are collected via eDiary and for EU, the primary endpoint and 3 secondary endpoints are collected via eDiary according to protocol design. Minimal disruption is expected for these endpoints because participants are expected to complete eDiary at home and submit the responses every day.

The secondary endpoints, MSQ v2.1 Role Function Restrictive domain score at Week 12 and HIT-6 total score at Week 12, will be collected using eTablet as one electronic patient reported outcome (ePRO) at site. Participants are required to complete the ePRO measures remotely at Visit 7 (Week 12) according to remote-visit procedure.

To evaluate the missing rate for this endpoint at Week 12, the number of participants who missed at least one ePRO assessment due to COVID-19 will be summarized at each visit in the efficacy analysis population of Off-Treatment Hypothetical Estimand (mITT population for US and Off-treatment Hypothetical Estimand population for EU respectively).

**Table 8. Summary of Collection Devices for Primary and Secondary Endpoints for Submission in the US**

Hypothesis Testing	Node	Endpoint	Collection Device
Primary	P1	Change from baseline in mean monthly migraine days across the 12-week treatment period	eDiary
Secondary 1	S1	Change from baseline in mean monthly headache days across the 12-week treatment period	eDiary
Secondary 2	S2	Change from baseline in mean monthly acute medication use days across the 12-week treatment period	eDiary
Secondary 3	S3	Achievement of at least a 50% reduction in mean monthly migraine days across the 12-week treatment period	eDiary
Secondary 4	S4	Change from baseline in MSQ v2.1 Role Function Restrictive domain score at Week 12	eTablet
Secondary 5	S5	Change from baseline in mean monthly Performance of Daily Activities domain score of the AIM-D across the 12-week treatment period.	eDiary
Secondary 6	S6	Change from baseline in mean monthly Physical Impairment domain score of the AIM -D across the 12-week treatment period.	eDiary

**Table 9. Summary of Collection Devices for Primary and Secondary Endpoints for European Submissions**

Hypothesis Testing	Node	Endpoint	Collection Device
Primary	P1	Change from baseline in mean monthly migraine days across the 12-week treatment period	eDiary
Secondary 1	S1	Change from baseline in mean monthly headache days across the 12-week treatment period	eDiary
Secondary 2	S2	Change from baseline in mean monthly acute medication use days across the 12-week treatment period	eDiary
Secondary 3	S3	Achievement of at least a 50% reduction in mean monthly migraine days across the 12-week treatment period	eDiary
Secondary 4	S4	Change from baseline in HIT-6 total score at Week 12	eTablet
Secondary 5	S5	Change from baseline in MSQ v2.1 Role Function Restrictive domain score at Week 12	eTablet

## 14.2 Safety and Other Evaluations

This section specifies analyses related to COVID-19 pandemic from the following aspects:

- Disposition
- Study visits and study procedures
- Protocol deviation
- Treatment interruption due to COVID-19
- TEAEs related with COVID-19 and supplemental signs and symptoms
- COVID-19 status (COVID-19 testing results or contact with a COVID-19 positive person)
- COVID-19 vaccine

Safety Population will be used for the planned analyses described above. The number of participants impacted by COVID-19 during the study will be summarized by treatment group and overall. In addition, the number of participants impacted by COVID-19 and

their corresponding disposition status in the double-blind treatment period and the follow-up period will be summarized respectively.

The number of participants who missed at least one entire visit, had impacted in-person clinic visits, and had remote visits using audio or video due to COVID-19 will be summarized by treatment group and overall. Furthermore, the number of participants who missed at least one assessment due to COVID-19 will be summarized by assessment category (laboratory, C-SSRS, urine pregnancy test, vital signs, ECG, and ePRO) and overall. Similar summaries will be provided by visit.

The number of participants with significant protocol deviation due to COVID-19 will be provided. The number of participants with study drug interruption due to COVID-19 will be provided as well. The number of participants with TEAEs related to COVID-19 infection and supplemental signs and symptoms will be provided.

The number and percentage of participants who received a COVID-19 vaccine will be tabulated by Anatomical Therapeutic Chemical (ATC) 4 class and preferred term (PT). The number and percentage of participants with TEAEs and serious TEAEs related to COVID-19 vaccine will be summarized by treatment and overall.

Supporting listings for the described analyses above will be provided.

